7.2.2 Description of Test Article

Study drug (test article) will be supplied as hard gelatin capsules for oral use at dose strengths of 25 and 100 mg or matching placebo. Excipients will include microcrystalline cellulose, lactose monohydrate, hypromellose 2910, crospovidone, colloidal silicon dioxide, magnesium stearate, and hard gelatin capsule. Infigratinib and the matching placebo will be manufactured under Good Manufacturing Practice (GMP) for investigational use.

The study center pharmacist or designee will dispense the correct number and dose strength of capsules to ensure the subject receives sufficient drug for each 28-day treatment cycle. Study drug will be dispensed to the subject by authorized trained study center personnel only.

7.2.3 Packaging and Labeling

Study drug capsules will be packaged in high-density polyethylene (HDPE) bottles with intact induction seal child-resistant closures. Medication labels will be in the local language and comply with the legal requirements of each country. Labels will include storage conditions for the drug.

7.2.4 Study Drug Accountability, Handling, and Disposal

Study drug capsules will be received by designated personnel at the study center, handled and stored safely and properly, and kept in a secured location to which only the investigator and

designated study center personnel have access. Upon receipt, study drug should be stored according to the instructions specified on the drug label and in the Investigator's Brochure. Refer to the Pharmacy Manual for further details.

The investigator or designee must maintain an accurate record of the shipment and dispensing of study drug in a drug accountability log. Subjects will be asked to return all used and unused bottles of study drug and packaging on a regular basis, at the end of the study, or at the time of study drug discontinuation. Drug accountability will be assessed by the investigator and/or study personnel, and captured in a subject drug accountability log. This information must be captured in the source document at each subject visit. Drug accountability will be completed by the field monitor during study center visits and at the completion of the study.

At study close-out, and, as appropriate during the course of the study, the investigator will provide access to all used and unused bottles of study drug, packaging, drug labels, and a copy of the completed drug accountability log to the field monitor.

At study close-out, study drug can be destroyed at the study center if permitted by local regulations. Alternatively, the study drug can be destroyed at a third-party depot.

7.2.5 *Dose Modifications for Study Drug*

Subject management and treatment decisions will be based upon Investigator evaluations.

7.2.5.1 *Dose Modifications and Delays*

For subjects who do not tolerate the protocol-specified dosing schedule, dose adjustments are permitted in order to allow the subject to continue the study treatment. For these subjects, the dosing guidelines outlined below will be followed. All dose modifications related to tolerability should be based on the worst preceding toxicity as described in [Table 6](#) (AEs considered possibly related to study drug) and [Table 7](#) (skin toxicity). In addition, per investigator's medical judgment, dose modification (hold) can be applied for subject's safety (eg, perioperatively); the medical monitor must be consulted for dose modifications that are not related to tolerability issues. Dosage changes must be recorded on the Dose Administration page of the eCRF.

The following guidelines should be applied.

- Each subject may be allowed up to 3 study drug dose reductions according to protocol-specified dose modifications for AEs. Prospective sponsor medical monitor approval is required for the third dose reduction ([Table 5](#)). Note: the minimum daily dose allowed in the study is 50 mg.
- Treatment-related toxicity will be managed as detailed in [Table 6](#), and additional guidelines in the protocol, or following institutional guidelines. Management of related toxicity, including during a period of study treatment hold, will continue until the toxicity is stable at Grade ≤ 1 , returns to baseline, or in accordance with the assessment of the treating physician.
- If treatment is resumed at the same dose of study drug, and the same toxicity recurs with the same or worse severity regardless of duration, dose must be reduced to the next lower dose

level. If treatment is resumed at the lower dose of study drug, and the same toxicity recurs with the same or worse severity, the subject should have a second dose reduction.

- Subjects who permanently discontinue the study drug for a study-related AE or an abnormal laboratory value must be followed up as described in Section [7.2.5.2](#).
- Study drug must be permanently discontinued for a delay of >14 days due to a treatment-related toxicity and may only be restarted with written permission of the medical monitor if (1) the delay is not due to an AE that requires permanent study drug discontinuation as provided in [Table 6](#), and (2) the subject has not met other criteria requiring study drug discontinuation as provided in Section [8](#), and (3) it is the investigator's opinion that no safety concerns are present. In situations where a delay of >14 days is needed for a treatment-related AE requiring permanent study drug discontinuation (see [Table 6](#)), with prospective sponsor medical monitor approval, the delay may be extended to a maximum of 28 days before permanent treatment discontinuation is required.
- If study drug is on hold for ≤ 14 days, and the criteria for restarting treatment are met, study treatment can be restarted on any day from D1 to D21 of a cycle. Study drug should not be restarted on D22 to D28 of a cycle; in such cases, treatment restart must wait until D1 of the next cycle.

Table 5: Dose Reduction Scheme

Dose Reduction	Starting Dose Level 0	Dose Level -1	Dose Level -2	Dose Level -3 ^a
Study drug	125 mg or matching placebo	100 mg or matching placebo	75 mg or matching placebo	50 mg or matching placebo

^a Dose reduction to 50 mg requires prospective sponsor medical monitor approval. Details are provided in the text above.

NOTE: The minimum daily dose of study drug allowed in the study is 50 mg.

Table 6: Criteria for Interruption and Re-initiation of Study Drug for Adverse Events Considered to be Possibly Related to Study Drug

Worst Toxicity CTCAE^a (version 5.0) Grade (Unless Otherwise Specified)	Dose Modifications any Time During a Cycle of Therapy
CARDIAC DISORDERS	
Cardiac – Prolonged QTcF Interval	
Grade 2: Average QTc 481 - 500 msec	
Maintain dose level of study drug.
 
Two additional ECGs separated by \geq5 minutes should be performed to confirm the finding. If the finding is confirmed, single ECG assessments should be performed for 2 additional cycles at the same frequency as in Cycle 1, or as clinically indicated. If abnormality is detected, 2 additional ECGs separated by at least 5 minutes should be performed to confirm the finding.
 
• If ECG assessments show no QTcF \geq481 msec, for subsequent cycles ECG monitoring will be performed according to the visit schedule.• If ECG assessments are still abnormal (QTcF \geq481 msec and \leq500 msec), then ECG monitoring must continue at the same frequency as in Cycle 1 for all subsequent cycles.
Grade 3: Average QTc \geq 501 msec; >60 msec change from baseline	
Hold dose of study drug. Two additional ECGs separated by at least 5 minutes should be performed to confirm the finding. If the finding is confirmed, monitor subject with hourly ECGs until the QTcF has returned to baseline and perform further monitoring as clinically indicated.
 
• Exclude other causes of QTcF prolongation such as hypokalemia, hypomagnesemia and decreased blood oxygenation.• Subjects should receive appropriate electrolyte replacement and should not receive further study drug until electrolytes are documented to be within normal limits. 
Once the QTcF prolongation has resolved to <481 msec, subjects may be re-treated at 1 lower dose level at the investigator's discretion. If not determined to be clinically significant, the subject may resume at the current dose.
 
Single ECG assessments should be performed for 2 additional cycles at the same frequency as in Cycle 1 or as clinically indicated. If abnormality is detected, 2 additional ECGs separated by at least 5 minutes should be performed to confirm the finding.
 
• If ECG assessments show no QTcF \geq481 msec, ECG monitoring will be performed according to the visit schedule for subsequent cycles.• If ECG assessments are still abnormal (QTcF \geq481 msec and \leq500 msec), then ECG monitoring must continue at the same frequency as in Cycle 1 or as clinically indicated, for all subsequent cycles.

Worst Toxicity CTCAE^a (version 5.0) Grade (Unless Otherwise Specified)	Dose Modifications any Time During a Cycle of Therapy
	
Subjects who experience recurrent QTcF \geq501 msec after 1 dose reduction will be discontinued from study treatment.
Grade 4: Torsade de pointes or polymorphic ventricular tachycardia or signs/symptoms of serious arrhythmia	Discontinue study drug.
INVESTIGATIONS-HEMATOLOGY	
Neutrophil Count Decreased (Neutropenia)	
Grade 3 (ANC <1000 - 500/mm ³ [$<1.0 - 0.5 \times 10^9/L$])	Hold dose of study drug until resolved to CTCAE Grade \leq 1 or baseline, then 
If resolved within \leq7 days, maintain dose level of study drug.If resolved between $>$7 days and 14 days, \downarrow 1 dose level of study drug.If not resolved within \leq14 days, discontinue study drug.
Grade 4 (ANC <500/mm ³ [$<0.5 \times 10^9/L$])	Hold dose of study drug until resolved to CTCAE Grade \leq 1, then \downarrow 1 dose level of study drug. If not resolved within \leq 14 days, discontinue study drug.
Febrile Neutropenia	
Grade 3 (ANC <1000/mm ³ with a single temperature of $>$ 38.3°C [101.0°F] or a sustained temperature of \geq 38.0°C [100.4°F] for $>$ 1 hour)	Hold dose of study drug until resolved to CTCAE Grade \leq 1, then 
If resolved within \leq14 days, \downarrow 1 dose level of study drug.If not resolved within 14 days, discontinue study drug
Grade 4	Discontinue study drug.
Anemia	
Grade 3 (hemoglobin <8.0 g/dL [$<4.9 \text{ mmol/L}$; $<80 \text{ g/L}$]; transfusion indicated)	Hold dose of study drug until resolved or corrected to CTCAE Grade \leq 1 or baseline, then maintain dose level.
Grade 4	Hold dose of study drug until resolved or corrected to CTCAE Grade \leq 1 or baseline, then \downarrow 1 dose level.
Platelet Count Decreased (Thrombocytopenia)	
Grade 3 (platelet <50,000 - 25,000/mm ³ [$<50 - 25 \times 10^9/L$])	Hold dose of study drug until resolved to CTCAE Grade \leq 1 or baseline, then 
If resolved within \leq7 days, maintain dose level of study drug.If resolved between $>$7 days and 14 days, \downarrow 1 dose level of study drug.If not resolved within \leq14 days, discontinue study drug.

Worst Toxicity CTCAE^a (version 5.0) Grade (Unless Otherwise Specified)	Dose Modifications any Time During a Cycle of Therapy
Grade 4 (platelet <25,000/mm ³ [$<25 \times 10^9/L$])	Hold dose of study drug until resolved to CTCAE Grade ≤ 1 or baseline, then \downarrow 1 dose level. 
• If not resolved within ≤ 14 days, discontinue study drug.
INVESTIGATIONS – RENAL	
Serum Creatinine	
Creatinine clearance <30 mL/min (calculated or measured)	Hold dose of study drug until creatinine clearance is ≥ 45 mL/min regardless of grade.
Serum creatinine increase Grade 2 ($\geq 1.5 - 3.0 \times$ ULN or $1.5 - 3.0 \times$ baseline)	Hold dose of study drug until resolved to Grade ≤ 1 or baseline, then: 
• If resolved within ≤ 7 days, maintain dose level of study drug.• If resolved between >7 days and 14 days, \downarrow 1 dose level of study drug• If not resolved within ≤ 14 days, discontinue study drug.
Serum creatinine increase Grade ≥ 2	If serum creatinine CTCAE Grade ≥ 2 has been demonstrated in conjunction with hyperphosphatemia, serum creatinine levels must be repeated at least weekly until resolution. 24-hour urine collection should be obtained as clinically indicated for total phosphate, calcium, protein, and creatinine clearance. Ultrasound examination of the kidneys should be performed as indicated to evaluate de-novo calcifications until resolution or stabilization of creatinine.
Serum creatinine increase Grade ≥ 3 ($>3.0 \times$ ULN or $>3.0 \times$ baseline)	Discontinue study drug.
INVESTIGATIONS – HEPATIC	
Blood Bilirubin Increased (for subjects with Gilbert Syndrome, these dose modifications apply to changes in direct bilirubin only)	
Grade 2 (bilirubin $> 1.5 - 3.0 \times$ ULN if baseline was normal; $>1.5 - 3.0 \times$ baseline if baseline was abnormal)	Hold dose of study drug until resolved to CTCAE Grade ≤ 1 , then: 
• If resolved within ≤ 7 days, maintain dose level of study drug.• If not resolved within ≤ 7 days, \downarrow 1 dose level of study drug.
Grade ≥ 3 (bilirubin $>3.0 \times$ ULN if baseline was normal; $>3.0 \times$ baseline if baseline was abnormal)	Discontinue study drug. Note: If CTCAE Grade 3 or 4 hyperbilirubinemia is due to hemolysis, then \downarrow 1 dose level of study drug and continue treatment at the discretion of the investigator.
AST or ALT Increased	
Grade 3 ($>5.0 - 20.0 \times$ ULN if baseline was normal; $>5.0 - 20.0 \times$ baseline if baseline was abnormal)	Hold dose of study drug until resolved to CTCAE Grade ≤ 1 or baseline, then: 
• If resolved within ≤ 7 days, \downarrow 1 dose level of study drug.• If not resolved within ≤ 7 days, discontinue study drug.
Grade 4 ($>20.0 \times$ ULN if baseline was normal; $>20.0 \times$ baseline if baseline was abnormal)	Discontinue study drug.

Worst Toxicity CTCAE ^a (version 5.0) Grade (Unless Otherwise Specified)	Dose Modifications any Time During a Cycle of Therapy
AST or ALT and Bilirubin Increased	
AST or ALT >3.0 - 5.0 × ULN and total bilirubin >2.0 × ULN without liver metastasis or evidence of disease progression in the liver	Hold dose of study drug until both transaminases and bilirubin resolved to CTCAE Grade ≤ 1 or baseline, then: 
• If resolved within ≤ 7 days, \downarrow 1 dose level of study drug.• If not resolved within ≤ 7 days, discontinue study drug.
AST or ALT >5.0 × ULN and total bilirubin >2.0 × ULN	Discontinue study drug
LABORATORY/METABOLIC DISORDERS	
Amylase and/or Lipase Increase	
General Comment:	A CT scan or other imaging study to assess the pancreas, liver, and gallbladder should be performed as clinically indicated within 1 week of the first occurrence of any CTCAE Grade ≥ 3 amylase and/or lipase.
Grade 3 (amylase or lipase >2.0 - 5.0 × ULN with signs or symptoms; >5.0 × ULN and asymptomatic)	Hold dose of study drug until resolved to CTCAE Grade ≤ 2 , then: 
• \downarrow 1 dose level of study drug.• If not resolved within ≤ 14 days, discontinue study drug. For recurrent Grade 3 asymptomatic lipase or amylase elevation despite dose reduction, study drug should be held and continuation of therapy should be discussed with the medical monitor following resolution to Grade ≤ 2 .
Grade 4 (amylase or lipase >5.0 × ULN and with signs or symptoms)	For any Grade 4 lipase or amylase elevation, study drug should be held and continuation of therapy should be discussed with the medical monitor following resolution to Grade ≤ 2 .
Hypophosphatemia	
Serum phosphate <LLN - 2.0 mg/dL (0.6 mmol/L)	Maintain dose level of study drug; decrease or hold dose of phosphate binder and optimize standard diet or medical therapy as clinically indicated to increase phosphate level.
Serum phosphate <2.0 - 1.0 mg/dL (<0.6 - 0.3 mmol/L)	Hold dose of study drug until resolved to >2.0 mg/dL (>0.6 mmol/L), then: 
• \downarrow 1 dose level of study drug.• If not resolved within ≤ 14 days, discontinue study drug.
Serum phosphate <1.0 mg/dL (<0.3 mmol/L) (life threatening consequences)	Discontinue study drug.
Hyperphosphatemia	
General Comment:	Optimize dose and schedule of phosphate lowering therapy in accordance with the package insert, or local or institutional guidelines.
Serum phosphate >5.5 - \leq 7.5 mg/dL	Maintain dose level of study drug and optimize phosphate-lowering therapy as clinically indicated.

Worst Toxicity CTCAE ^a (version 5.0) Grade (Unless Otherwise Specified)	Dose Modifications any Time During a Cycle of Therapy
Serum phosphate >7.5 mg/dL for >7 days despite maximal phosphate-lowering therapy Or, single serum phosphate >9.0 mg/dL regardless of duration or dose of phosphate-lowering therapy	
 Hold dose of study drug until resolved to serum phosphate ≤5.5 mg/dL. Restart study drug at the same dose level with maximal phosphate binder dosing if the subject did not receive maximal phosphate binder dosing for serum phosphate >7.5 mg/dL for >7 days. ↓ 1 dose level of study drug if the subject had received maximal phosphate-lowering therapy for serum phosphate >7.5 mg/dL for >7 days or if subject had a one-time serum phosphate of >9.0 mg/dL. Restart study drug with maximal phosphate binder dosing. 
It is recommended that phosphate binder dosing continues during study drug dose interruptions for hyperphosphatemia and that serum phosphate values be monitored frequently, eg, every 2-3 days.
 
 Phosphate binder dosing should be held during the week off of study drug each cycle (Days 22-28) unless serum phosphate is not normalized and during study drug dose interruptions for non-hyperphosphatemia AEs.
Serum phosphate with life-threatening consequences; urgent intervention indicated (eg, dialysis)	Discontinue study drug.
Hypercalcemia	
Serum calcium Grade 2 Corrected serum calcium (>11.5 - 12.5 mg/dL [>2.9 - 3.1 mmol/L]) Ionized calcium (>1.5 - 1.6 mmol/L) symptomatic	
Hold dose of study drug until resolved to Grade 1 or baseline, then:
 
 If resolved within ≤7 days after suspending study drug, maintain dose level. If resolved between >7 days and 14 days, ↓ 1 dose level. If not resolved within ≤14 days, discontinue study drug.
Serum calcium Grade ≥3 Corrected serum calcium (>12.5 - 13.5 mg/dL [>3.1 - 3.4 mmol/L]) Ionized calcium (>1.6 - 1.8 mmol/L), hospitalization indicated	Discontinue study drug.
GASTROINTESTINAL SYSTEM DISORDERS	
Pancreatitis	
Grade 2 (asymptomatic enzyme elevation with radiologic findings only)	
Hold dose of study drug until resolved to CTCAE Grade <2, then:
 
 ↓ 1 dose level of study drug. If not resolved within ≤14 days, discontinue study drug. 
For recurrent Grade 2 asymptomatic radiologic pancreatitis despite dose reduction, discontinue study drug.

Grade 3 or Grade 4	Discontinue study drug.
Diarrhea	
General Comment:	Antidiarrheal medication is recommended at the first sign of abdominal cramping, loose stools, or overt diarrhea.

Worst Toxicity CTCAE^a (version 5.0) Grade (Unless Otherwise Specified)	Dose Modifications any Time During a Cycle of Therapy
Grade 1 (increase of <4 stools/day over baseline; mild increase in ostomy output compared to baseline)	Maintain dose level of study drug, initiate antidiarrheal treatment.
Grade 2 (increase of 4-6 stools/day over baseline; moderate increase in ostomy output compared to baseline; limiting instrumental activities of daily living [ADL])	
 Hold dose of study drug until resolved to CTCAE Grade ≤ 1. Optimize antidiarrheal treatment. For reoccurrence of diarrhea CTCAE Grade 2, hold dose of study drug until resolved to CTCAE Grade ≤ 1, then \downarrow study drug by 1 dose level.
Grade 3 (increase of ≥ 7 stools/day over baseline; hospitalization indicated; severe increase in ostomy output compared to baseline; limiting self-care ADL)	
 Hold dose of study drug until resolved to CTCAE Grade ≤ 1. Optimize antidiarrheal treatment. \downarrow study drug by 1 dose level. For reoccurrence of diarrhea CTCAE Grade 3, despite optimal antidiarrheal treatment, discontinue study drug.
Grade 4	Discontinue study drug.
Vomiting	
Grade 2 (outpatient IV hydration; medical intervention indicated) not controlled by optimal anti-emetic therapy	Hold dose of study drug until Grade ≤ 1 , then \downarrow 1 dose level. 
 If not resolved within ≤ 14 days, discontinue study drug.
Grade 3 (tube feeding, TPN, or hospitalization indicated) not controlled by optimal anti-emetic therapy or Grade 4	Discontinue study drug.
EYE DISORDERS (CONFIRMED BY OPHTHALMOLOGIC EXAMINATION)	
Retinal Disorders	
Grade 2 or 3 central serous retinopathy and central serous retinopathy-like events	Hold dose of study drug until resolved to Grade ≤ 1 and continue ophthalmic evaluations. 
 If resolved within ≤ 14 days, \downarrow study drug by 1 dose level. If not resolved within ≤ 14 days, discontinue study drug.
Grade ≥ 1 retinal vein occlusion, Grade 4 central serous retinopathy and central serous retinopathy-like events	Discontinue study drug.
Other Ocular/Visual Toxicity	
Grade ≥ 3	Hold dose of study drug until resolution to Grade ≤ 1 . 
 If resolution within ≤ 14 days, \downarrow 1 dose level. If not resolved within ≤ 14 days, discontinue study drug.
OTHER CLINICALLY SIGNIFICANT AEs	
Grade 3	Hold dose of study drug until resolved to CTCAE Grade ≤ 1 , then \downarrow 1 dose level of study drug. 
 If not resolved within ≤ 14 days, discontinue study drug.
Grade 4	Discontinue study drug.

Abbreviations: ADL=activities of daily living; AE=adverse Event; ALT=alanine aminotransferase; ANC=absolute neutrophil count; AST=aspartate aminotransferase; CT= computed tomography; CTCAE=Common Terminology Criteria for Adverse Events; ECG=electrocardiogram; IV=intravenous;

LLN=lower limit of normal; QT=measure of time between the start of the Q wave and the end of the T wave (QT interval) in the heart's electrical cycle; QTc=QT interval corrected for heart rate; QTcF=QTc corrected by Fridericia's formula; ULN=upper limit of normal.

^a CTCAE (v5.0) general guidelines:

Grade 1: Mild; asymptomatic or mild symptoms; clinical or diagnostic observations only; intervention not indicated.

Grade 2: Moderate; minimal, local or noninvasive intervention indicated; limiting age-appropriate instrumental ADL.

Grade 3: Severe or medically significant but not immediately life-threatening; hospitalization or prolongation of hospitalization indicated; disabling; limiting self-care ADL.

Grade 4: Life-threatening consequences; urgent intervention indicated.

Grade 5: Death related to AE.

NOTE: All dose modifications should be based on the worst preceding toxicity. Subjects may have a third dose reduction only with prospective approval of the sponsor medical monitor.

7.2.5.2 *Follow-up for Toxicities*

Subjects whose study drug is interrupted or permanently discontinued due to an AE or clinically significant laboratory value must be followed up at least once a week (or more frequently if required by institutional practices, or if clinically indicated) for 4 weeks, and subsequently at 4-week intervals, until resolution or stabilization of the event, whichever comes first. Clinical experts or specialists, such as an ophthalmologist, endocrinologist, dermatologist, should be consulted as deemed necessary. Further guidelines and dose modifications for the management of specific study drug-induced toxicities (hyperphosphatemia, diarrhea) are provided in [Table 6](#). All subjects must be followed up for AEs and SAEs for 30 days following last dose of study drug.

7.2.6 *Anticipated Risks and Safety Concerns for Infigratinib*

Eligibility criteria as well as specific dose modification and stopping rules are included in this protocol. Guidelines for prophylactic or supportive treatment for expected toxicities, including management of study drug-induced AEs (eg, hyperphosphatemia, renal toxicities) are provided in [Table 6](#) and Section [7.5](#). For more information, refer to the nonclinical toxicity and/or clinical data presented in the infigratinib Investigator's Brochure.

Treatment of AEs or lab abnormalities should follow the protocol where specified, otherwise local institutional guidelines with regard to safety management should apply.

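### For three toxicities that recur after a dose reduction, Section 7.2.5.1 calls for a second reduction while Table 6 orders discontinuation, and the protocol does not say which text governs

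*Protocol*

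**What the plan says.** Section 7.2.5.1 of the protocol gives general guidelines for dose changes, and one bullet deals with recurrence. If the event returns after treatment was resumed at the same dose, the dose must go down one level. If treatment was resumed at the lower dose and "the same toxicity recurs with the same or worse severity, the subject should have a second dose reduction". No toxicity is excepted. The first bullet sets the overall allowance: "Each subject may be allowed up to 3 study drug dose reductions according to protocol-specified dose modifications for AEs", with medical monitor approval needed for the third. Table 5 gives the levels as 125, 100, 75 and 50 mg.

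Table 6 has its own recurrence rules in some rows:

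- QTcF: subjects with a recurrence at or above 501 "msec after 1 dose reduction will be discontinued from study treatment".
- Diarrhea: "For reoccurrence of diarrhea CTCAE Grade 3, despite optimal antidiarrheal treatment, discontinue study drug". In this row the first Grade 3 episode already carries a one-level reduction.
- Pancreatitis: "For recurrent Grade 2 asymptomatic radiologic pancreatitis despite dose reduction, discontinue study drug".
- Amylase and lipase: for recurrent Grade 3 asymptomatic elevation "despite dose reduction, study drug should be held and continuation of therapy should be discussed with the medical monitor", once the elevation has resolved to Grade 2 or lower.

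Section 7.2.5.1 also sends the reader to Table 6. Its introduction bases tolerability changes on Tables 6 and 7, and one bullet begins "Treatment-related toxicity will be managed as detailed in" Table 6. The same sentence then adds the protocol's other guidelines and institutional guidelines as further sources. Section 7.5.3, on diarrhea, refers to Table 6 for dose changes. It then says that where antidiarrheal agents do not bring the diarrhea to a tolerable level, treatment should be paused temporarily or the dose lowered.

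**The concern.** The recurrence bullet and the three discontinuation rows describe the same patient: one dose reduction already made, and the same toxicity back at the same severity. One text keeps that patient on drug at the next lower level; the other takes the patient off. A site that follows either text to the letter departs from the other.

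The events are repeat QTc prolongation, repeat radiologic pancreatitis and repeat severe diarrhea, so continuing or stopping is a safety decision. There is also an analysis consequence. SAP Section 8.10.1 tabulates adverse events leading to discontinuation, and SAP Section 8.10.3 summarizes treatment duration, cumulative dose and relative dose intensity. All of these depend on which instruction a site followed.

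**Working it through.** The plan gives no figure to reproduce. The check sets each Table 6 recurrence rule beside the general bullet.

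| Recurrent event after one reduction | Section 7.2.5.1 bullet | Table 6 | Relation |
|---|---|---|---|
| QTcF of 501 msec or more | second reduction | discontinue | opposed |
| Grade 3 diarrhea, despite optimal antidiarrheal treatment | second reduction | discontinue | opposed |
| Grade 2 asymptomatic radiologic pancreatitis | second reduction | discontinue | opposed |
| Grade 3 asymptomatic lipase or amylase elevation | second reduction | hold, then discuss continuation | different, not opposed |

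**Do the triggers overlap?** For QTcF, Table 6 lets the investigator re-treat one level lower, or at the current dose if the finding is not clinically significant. The conflict arises on the first path only. For diarrhea it arises only when antidiarrheal treatment was already optimal. For pancreatitis it is confined to Grade 2 asymptomatic radiologic events. Within those limits, each Table 6 condition falls inside the bullet's condition, so both instructions apply at once.

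**Does another passage rank them?** Four places were checked.

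1. The pointers to Table 6 in Section 7.2.5.1 name it as a source. One of them joins it to other guidelines without an order of precedence.
2. The bullet on delays beyond 14 days does treat a Table 6 permanent discontinuation as a bar to restarting, subject to its own extension clause. The recurrence bullet has no such cross-reference.
3. The list of mandatory discontinuations in Section 8.1.1 does not name the Table 6 recurrence rules. Its nearest item is an adverse event that substantially alters the individual risk-benefit balance.
4. Section 7.5.3 tells sites to interrupt or reduce for uncontrolled diarrhea, with no mention of grade or recurrence. Beside the Grade 3 diarrhea row it is a third text, closer to the bullet than to the row.

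**Which summaries can move?** Under the bullet, the subject does not enter the discontinuation table for this event; under Table 6, the subject does. Duration and cumulative dose continue to accrue or stop accordingly. Relative dose intensity also moves. In the example in SAP Section 6, the planned dose accrues at 125 mg for each dosing day until treatment ends. A subject who started at 125 mg and takes a second reduction to 75 mg therefore adds later dosing days at 75/125 = 0.60. A subject stopped at the recurrence adds no further days to numerator or denominator.

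**The case against.** The strongest reply is that a specific rule displaces a general one. Section 7.2.5.1 sends tolerability changes to Table 6 and, in the delay bullet, treats Table 6 discontinuations as binding. The recurrence bullet is one of a set of guidelines and says *should*, while the QTcF row says *will be*. Many Table 6 rows, such as neutropenia, have no recurrence rule, so the bullet can be read as the default for those rows. A careful site may well read it that way.

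That makes the gap mainly a missing statement of precedence, and this part of the reply stands. It does not remove the conflict. The protocol never states that reading, the recurrence bullet does not defer to Table 6 as the delay bullet does, and Section 7.5.3 points the other way for diarrhea.

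A reader might also count four opposed rows. The documents support three: a hold followed by a discussion about continuing, as in the lipase and amylase row, leaves room for a further reduction.

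**Conclusion.** The inconsistency is real and limited. Three Table 6 rows are opposed to the recurrence bullet, one further row differs in wording, and Section 7.5.3 adds to the uncertainty for diarrhea. The conclusion rests on a literal reading of the bullet and on taking *discontinue* in Table 6 as permanent, in contrast to *hold*.

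The documents give no recurrence rates, so the number of subjects affected cannot be stated. Three stronger inferences are tempting and not supported:

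- *That the Phase 1 rate of Grade 3/4 hyperlipasemia in Section 3.4.2 (6.7%) measures the problem.* It concerns only the row that is not opposed, is counted regardless of relationship to treatment, and is not a recurrence rate.
- *That the effect falls almost only in the infigratinib arm.* No placebo rates are given for these events, and Section 7.6.1 reports that preliminary data show no effect of infigratinib on ECG intervals.
- *That counts of adverse events leading to dose reduction would change.* SAP Section 8.10.1 counts subjects and combines reduction with interruption. Anyone reaching the second-reduction step has already had a reduction for the same toxicity, so is already in that table.

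The definition of disease-free survival and the intent-to-treat set do not depend on this point, since subjects stay in follow-up after stopping study drug (Section 8.1.1). SAP Sections 1 and 8.1 record early closure and an analysis without formal efficacy testing. What remains is the reading of the discontinuation and exposure tables, the safety of any continued dosing, and reuse of this text in another protocol.

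**What to change.** Reconcile the recurrence bullet in Section 7.2.5.1, the recurrence rules in Table 6 and the diarrhea text in Section 7.5.3, so that one action follows a given repeat event. State in the bullet which text governs when a Table 6 row has its own recurrence rule. The sponsor's clinicians choose the rule; this review takes no position on it.

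The same drafting should settle what the bullet means by a recurrence of *worse* severity, because Table 6 discontinues at higher grades in other rows, for example Grade 4 diarrhea and serum creatinine increase of Grade 3 or higher.

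If dosing continues anywhere, this costs about one sentence in an amendment or clarification letter, plus an aligning edit to Section 7.5.3. If dosing has ended, a short note in the study report that sites had two instructions for these events would serve readers of the discontinuation and exposure tables.
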